11.6.3 Safety Alerts

Three months after the first subject is enrolled in the study, and at the end of each 3-month period thereafter, if any SAEs (expected or unexpected) have been reported in the study during the preceding 3 months, the SDMC will:

- Use the current version of the MedDRA dictionary to code all AEs (serious or not) that have been recorded on study AE forms.
- Make a “snapshot” copy of the AE data, including MedDRA codes.
- Create frequency tables of treatment x occurrence (yes or no, since inception of the study) of all subjects. One table will be created for each highest level MedDRA term for which SAEs have been reported. The counting units are subjects, not events.
- Compute Fisher’s Exact Test (FET) statistic to test the alternative hypothesis that occurrence of SAEs is not independent of treatment group. The FET p-value is not adjusted for multiplicity.
- If the FET p-value is less than the critical value shown in Table 11.3 and the active treatment group has a higher AE rate, the SDMC will conduct further statistical analyses as indicated by the circumstances and report the results to the Chair of the DSMB subcommittee monitoring this study, the PI, and the NHLBI Project Officer.

The SDMC will not file a report of all SAEs if none of the FET p-values is less than the critical value shown in Table 11.4 or if the relative risk is less than 1.

11.6.4 Reporting of All Adverse Events (Serious and Non-serious)

Six months after the first subject is enrolled in the study, and at the end of each 6 month period thereafter, the SDMC will:

- Use the current version of the MedDRA dictionary to code all AEs that have been recorded on study AE forms.
- Make a “snapshot” copy of the AE data, including MedDRA codes.

- Create frequency tables of treatment x occurrence (yes or no, since inception of the study) of all subjects. One table will be created for each highest-level MedDRA term for which AEs have been reported. The counting units are subjects, not events.
- Compute Fisher's Exact Test (FET) statistic to test the alternative hypothesis that occurrence of AEs is not independent of treatment group. The FET p-value is not adjusted for multiplicity.
- If the FET p-value is less than the critical value shown in Table 11.3 and the active treatment group has a higher AE rate, the SDMC will conduct further statistical analyses as indicated by the circumstances and alert the DSMB to this finding in the semi-annual DSMB report.
- Collaborate with the PI to incorporate the results into the study's semi-annual report to the DSMB and the NHLBI Project Officer.

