7.1.2 Description of Type of Study

This is a multi-center, randomized, double-blind, placebo-controlled Phase III clinical trial that will include at least 56 subjects with SCD who are hospitalized for ACS. Individuals who meet entry criteria will be randomized to receive either dexamethasone or placebo. Dexamethasone will be administered initially as 0.3 mg/kg by mouth every 12 hours for a maximum of 4 doses (2 days) or until discharge from the hospital, whichever occurs first. Afterward, the study drug will be tapered over 6 days for a total duration of therapy not to exceed 8 days. Due to possible age-related and ACS severity-related differences in the duration of signs and symptoms of ACS, randomization will be stratified by age and severity of ACS (see Section 8.3). We are enrolling a maximum of 112 pediatric subjects. We will enroll adult subjects at the rate site participation will allow, which we anticipate will be no more than 56 subjects. Interim analyses will be performed when a total of 56 subjects and 112 subjects have completed their hospital stay. If we do not stop enrollment after these interim analyses are completed, we will continue to enroll up to a maximum total of 112 pediatric subjects. The efficacy and safety of dexamethasone will be compared to placebo in the context of standard supportive care for ACS.

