9.2 Randomization and Masking

After enrollment, subjects will be randomized to one of two treatment arms. Subjects in Arm 1 will receive oral dexamethasone. Subjects in Arm 2 will receive oral placebo. A computer-generated, adaptive randomization schema will be used to allocate subjects 1:1 between the two treatment arms. Randomization will be stratified by site, age and the severity of ACS (see Section 8.3). In order to increase the likelihood of balance in treatment allocations, subjects will be randomized using the standardized range variation (79) of the sequential allocation algorithm of Pocock and Simon (80), a minimization method. This method attempts to achieve treatment balance on several subject characteristics (i.e. age group, site, and severity of ACS in this study) simultaneously – not within separate strata. Minimization consists of biasing the treatment allocation so as to minimize the total imbalance between the treatment groups on some scale (81). The order of entry of the subjects to the various centers and in the various prognostic groups is assumed to be random. As minimization is a dynamic method that uses information on subjects already entered to allocate treatment to the next subject, a continuous updating of the information related to previous treatment allocations is required, thus a centralized randomization system will be used.

Pharmacists at each center will be unblinded and will utilize information from the interactive voice/web randomization system (IVRS) at the SDMC to obtain a new treatment assignment for a subject and provide each subject with appropriate dosing of both therapies. The IVRS system has the capability of providing unblinding information in case of a medical emergency where the exact study drug is needed in order to appropriately treat a subject.

The time interval between Randomization and the first dose of study drug administration will be no longer than 2 hours. In the event a subject's first dose occurs outside the 2-hour time limit, the subject will still be included in the study and the analysis. This is in the spirit of the intention-to-treat analysis. The amount of time in excess of the 2-hour limit until the first dose of study drug will also be recorded. This event will be documented as a protocol deviation.

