The subject's physicians, nurses, and ancillary support staff will not be aware of the treatment assignment. The placebo formulations will be identical in appearance and taste to the active compounds (see Section 9.1.3).

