11.6.5 Reporting of Adverse Clinical Laboratory Trends

An *adverse clinical laboratory trend* is a shift, in an adverse direction, of a clinical laboratory parameter that is more adverse in an active treatment group than in a control group (e.g., mean ALT change-from-baseline increases significantly more in the active treatment group than in the control group or a higher proportion of subjects with an abnormal reading in the active treatment group than in the control group).

Six months after the first subject is enrolled in the study, and at the end of each 6 month period thereafter, the SDMC will:

- Make a "snapshot" copy of the study's clinical laboratory data.
- Perform an appropriate statistical analysis of clinical laboratory data for each clinical laboratory evaluation obtained in this study.
- Perform an appropriate statistical test. If the hypothesis test p-value is less than the critical value shown in Table 11.4, the SDMC will conduct further statistical analyses as indicated by the circumstances and highlight this finding in the semi-annual DSMB report. Collaborate with the PI to

incorporate the results into the study's semi-annual report to the DSMB and the NHLBI Project Officer.

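### In a double-blind trial, the study's Principal Investigator co-writes by-treatment AE and laboratory results every 6 months and receives by-treatment SAE and rebound results whenever a quarterly alert fires

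*Protocol*

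**What the plan says.** Section 7.1.2 describes a "multi-center, randomized, double-blind, placebo-controlled Phase III clinical trial". Section 9.2 says of the staff in contact with subjects that the "physicians, nurses, and ancillary support staff will not be aware of the treatment assignment". The one group it names as an exception is the dispensing staff: "Pharmacists at each center will be unblinded".

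Section 11.6 then sets up safety reporting by arm:

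- **All AEs, every 6 months (11.6.4).** The SDMC is told to "Create frequency tables of treatment x occurrence (yes or no, since inception of the study) of all subjects", run Fisher's exact test, and "Collaborate with the PI to incorporate the results into" the semi-annual report to the DSMB and the NHLBI Project Officer. No condition is attached to that last step.
- **Laboratory trends, every 6 months (11.6.5).** The same collaboration is required. The trend of interest is a shift that is "more adverse in an active treatment group than in a control group".
- **SAEs, every 3 months (11.6.3).** If the p-value crosses the critical value and the active arm has the higher rate, the SDMC must "report the results to the Chair of the DSMB subcommittee monitoring this study, the PI, and the NHLBI Project Officer".
- **Rebound, every 3 months (11.6.6).** The recipients are the same, with a threshold of p below 0.025 and the active arm higher.

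Sections 11.6 and 11.6.2 also name the PI as an alternative to the SDMC as maker of these reports. No section describes a closed report that is kept from the PI.

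**The concern.** The PI in these sections is the study lead. Section 11.6 has this person pass NHLBI's decisions to all participating investigators, and Section 11.2.1 refers to site Principal Investigators separately. Someone in that position influences how the trial is run while it is still enrolling. Blinding such a person to accumulating between-arm results is a basic protection, and the usual means is to split the DSMB report into a closed by-arm part and an open pooled part.

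Here the protocol assigns the PI a part in the by-arm material. This is not a detail left for a later document. One monitored outcome, rebound hospitalization, is also a secondary endpoint (7.1.1), and preventing it with the taper is a stated objective (6.2). What is at stake is the credibility of decisions taken while the lead knows how the arms compare on safety.

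**Working it through.** The point concerns who receives what, so the main check sets the reporting rules side by side. The arithmetic only sizes timing and frequency.

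**1. What reaches the PI**

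| Analysis | Frequency | By arm? | Reaches the PI |
|---|---|---|---|
| All AEs (11.6.4) | 6 months | Yes | Always |
| Laboratory trends (11.6.5) | 6 months | Yes | Always |
| SAEs (11.6.3, Table 11.4) | 3 months | Yes | Only if p < 0.01 and active arm higher |
| Rebound (11.6.6) | 3 months | Yes | Only if p < 0.025 and active arm higher |
| Primary endpoint and conditional power (13.2.4) | Interims | Yes | No PI role stated; conditional power goes to the DSMB |

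**2. Would coding the arms help?** The protocol does not say whether arms are coded. For alerts, coding would not hide the direction, because the rule fires only when the active arm is worse. For a routine report without an alert, coding could hide it.

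**3. Timing.** Appendix 2 expects 112 subjects in 15 months: 112 / 15 = 7.47 per month, or 22.4 per quarter (Appendix 2 uses 22). Semi-annual reports then fall at 2 × 22 = 44 and 4 × 22 = 88 subjects. Section 13.2.4 places the interim analyses at 56 and 112, so each routine report precedes one. If enrollment went on to 112 children plus the anticipated ceiling of 56 adults (7.1.2), then 168 / 7.47 = 22.5 months, which adds a report at month 18.

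**4. How often would the rebound route operate?** Appendix 2 prints alert rates of 68%, 94% and 19% for dexamethasone rebound of 25%, 30% and 10% against 5% on placebo, but for a chi-square test at 0.05. Simulating that test on cumulative data without continuity correction gives 84%, 94% and 21%: the second and third are close, the first is not reproduced. In any case it is not the rule in 11.6.6. For the 11.6.6 rule the inputs were Fisher's exact test, p < 0.025 with dexamethasone higher, cumulative looks at 22, 44, 66 and 88 subjects in equal arms, and 10,000 trials per scenario. The chance of at least one alert is:

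| Dexamethasone v placebo | Chance of an alert |
|---|---|
| 25% v 5% | 59% |
| 30% v 5% | 80% |
| 10% v 5% | 4% |
| 5% v 5% | 0.2% |
| 2.5% v 5% | about 0% |

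This route is rarely used unless rebound returns at about the rates of the two earlier studies (27% and 31% on dexamethasone, per Appendix 2).

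**5. Is the PI needed?** Section 11.9.1 has the SDMC generate the safety report, and Section 12.2 has its host organization run the analyses and prepare the DSMB report, neither mentioning the PI. Section 11.6 sends DSMB advice to NHLBI, which decides and then notifies the PI. Safety oversight does not depend on the PI seeing by-arm tables.

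**The case against.** The best defense is that aggregate tables reveal no subject's assignment, that Section 9.2 masks bedside staff to assignment rather than the PI to pooled comparisons, and that the SDMC does the analysis, so the PI's collaboration might be editorial. The first two statements are accurate. The third is possible, but the text says the results are what the PI helps incorporate, and nothing limits that.

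A reader might infer more than the documents support:

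- **That by-arm results reach the PI every 3 months.** They do not. The quarterly analyses reach the PI only on an alert.
- **That the PI sees efficacy.** The primary endpoint is in none of these reports. Section 11.2 keeps expected signs and symptoms of the disease under study out of the AEs unless unusually severe, and the tables are built at the highest MedDRA level. The clear overlap is rebound, on an alert.
- **That leukocyte counts would give the arms away.** Section 5 reports that peak counts did not differ by arm in the earlier study examined.
- **That endpoint assessment is biased.** This would need a PI who also treats subjects, which is not stated. Rebound is counted in the week after discharge (10.3.3), when that subject's primary endpoint is already fixed.
- **That the PI could steer amendments.** Section 14.2.1 has NHLBI initiate protocol changes.

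These limits stand and narrow the harm. They do not explain why the lead of a double-blind trial should co-write by-arm results.

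**Conclusion.** The point holds in a limited form. The protocol gives the study-level PI aggregate by-arm AE and laboratory results routinely, at about 44 and 88 subjects on its own accrual assumption, and by-arm SAE and rebound results when an alert fires. For rebound, the chance of at least one alert runs from about 0.2% at equal 5% rates to 80% at 30% v 5%.

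Individual assignments stay masked and the primary endpoint is not disclosed. No effect on type I error, power or the treatment estimate has been shown. The exposure is to trial-level conduct, and would extend further only if the PI also treats subjects. This is a cheap improvement worth making, not a flaw that must be repaired before the trial can be relied on.

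The conclusion assumes that the PI in Section 11.6 is the study lead, that accrual follows Appendix 2, and that the 11.6.6 alert rule is the one in its bullet list. The closing sentence of 11.6.6 says no report is filed when p is below 0.025, which contradicts that bullet and needs reconciling.

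**What to change.** In Sections 11.6 and 11.6.2 to 11.6.6:

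- Remove the PI as co-author or recipient of any result shown by treatment.
- Have the SDMC send alerts and a closed by-arm semi-annual report to the DSMB and the NHLBI Project Officer only.
- Give the PI an open report with the arms pooled, plus individual SAE narratives without assignment.
- State that the PI learns of any safety action through the DSMB-to-NHLBI route already in Section 11.6.

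Individual SAE reporting under 11.6.1 is unaffected. The cost is protocol wording and splitting a report that the SDMC already produces, with no new data. The one real loss is that the PI can no longer comment on by-arm tables, so the DSMB must rely on its own clinical members to interpret them.

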11.6.5 Reporting of Adverse Clinical Laboratory Trends

An *adverse clinical laboratory trend* is a shift, in an adverse direction, of a clinical laboratory parameter that is more adverse in an active treatment group than in a control group (e.g., mean ALT change-from-baseline increases significantly more in the active treatment group than in the control group or a higher proportion of subjects with an abnormal reading in the active treatment group than in the control group).

Six months after the first subject is enrolled in the study, and at the end of each 6 month period thereafter, the SDMC will:

- Make a "snapshot" copy of the study's clinical laboratory data.
- Perform an appropriate statistical analysis of clinical laboratory data for each clinical laboratory evaluation obtained in this study.
- Perform an appropriate statistical test. If the hypothesis test p-value is less than the critical value shown in Table 11.4, the SDMC will conduct further statistical analyses as indicated by the circumstances and highlight this finding in the semi-annual DSMB report. Collaborate with the PI to

incorporate the results into the study's semi-annual report to the DSMB and the NHLBI Project Officer.

Adverse Clinical Lab Trends	SDMC performs semi-annual analyses of clinical lab change-from-baseline using analyses appropriate for the data type. Report every 6 months. Alert only when $p < \text{critical value}$ and change is in "adverse" direction.	$p < 0.005$ p not adjusted for multiplicity

11.7 Subject Discontinuation due to AE(s)

The following criteria will be used to determine whether or not subjects exhibit toxicities of the study drug(s) sufficient to require discontinuation from the study.

We will closely monitor signs, symptoms, and laboratory findings to assess for unexpected toxicities. Oral dexamethasone will be discontinued in any subject who experiences the following:

1. New hypertension (not pre-existing) that requires treatment with antihypertensive medications;
2. Stroke;

3. Gastrointestinal hemorrhage; or
4. Pregnancy.

In addition, subjects will also have dexamethasone discontinued if they become unable to orally ingest dexamethasone or, at the request of the subject, for any reason. In the event that dexamethasone is stopped, subjects will continue to be followed by study personnel to assess for potential side effects of dexamethasone administration.

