6 STUDY OBJECTIVES AND PURPOSE

6.1 Primary Objective:

To determine whether dexamethasone decreases the duration of signs and symptoms of ACS. The duration of ACS will be assessed by ACS Assessment (Appendix 3) that incorporate the resolution of tachypnea, hypoxemia, increased work of breathing, and thoracic pain as well as the cessation of medical interventions to support respiration. We predict that dexamethasone will decrease the time to pulmonary recovery.

6.2 Secondary Objectives:

To determine whether dexamethasone reduces morbidity associated with ACS. We predict that dexamethasone will decrease subjects' pain, the requirement for opioid analgesics, the number of transfusions, the use of supplemental oxygen, the duration of hypoxemia, the duration of hospitalization, and the duration of fever.

To determine whether a tapered regimen of dexamethasone prevents rebound VOC. We will study whether a tapered regimen of oral dexamethasone prevents the recurrence of ACS or the development of other VOC soon after ACS. Abrupt discontinuation of a short course of IV corticosteroid may precipitate an early relapse of VOC. As such, we wish to determine whether a longer, tapered course of oral dexamethasone can prevent the relapse of ACS or VOC and readmission to the hospital. We will also document any treatment-related toxicities.

To determine whether dexamethasone modulates the endothelial phenotype to a less proadhesive and procoagulant state, and to determine whether the discontinuation of dexamethasone will be associated with a rebound in the expression of endothelial activation markers of adhesion and coagulation. We predict that the dexamethasone-treated group will demonstrate a decrease (compared to admission values) in plasma levels of VCAM₁, ICAM₁, P-selectin, whole blood tissue factor (WBTF), tissue factor- (TF-) and VCAM₁-positive endothelial microparticles, and ultra-large vWF multimers (vWF/ULVF) at the 48 hour and discharge blood samplings. Inter-group comparisons (placebo vs dexamethasone) will also demonstrate a decrease following dexamethasone when compared to placebo-treated controls. We also predict that the dexamethasone-treated subject group may demonstrate a rebound in plasma levels of VCAM₁, ICAM₁, P-selectin, vWF, WBTF, and TF and VCAM₁-positive endothelial microparticles concomitant with steroid discontinuation.

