8.3 Stratification

Before randomization, subjects will be stratified by site, age (< 18 years or ≥ 18 years) and by severity of ACS (defined below). Stratification by age and severity of ACS will be done to ensure balance across treatment groups. Strata will not be adequately sized (i.e., powered) to analyze the primary endpoint in each stratum.

Mild to moderately severe ACS is defined by all the diagnostic criteria for ACS listed in the subject eligibility section in addition to the following:

- transcutaneous oxygen saturation of ≥ 85% in room air, and
- segmental or lobar infiltrates that involve no more than two lobes by chest radiography.

Severe ACS is defined by all the diagnostic criteria for ACS listed in the subject eligibility section and one or more of the following:

- impending respiratory failure or need for invasive or non-invasive ventilatory support,

- transcutaneous oxygen saturation of $< 85\%$ in room air or $\leq 90\%$ despite maximal supplemental oxygen, or
- segmental or lobar infiltrates that involve three or more lobes by chest radiography.

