8.4 Subject Discontinuation

Subjects may decide to discontinue participation at any time during the study.

Investigators may discontinue any subject at their discretion if, in their professional opinion, the subject's health, safety, and/or well-being is threatened by continued participation in the study. The following circumstances require discontinuation of subjects:

1. New hypertension (not pre-existing) that requires treatment with antihypertensive medications;
2. Stroke;
3. Gastrointestinal hemorrhage; and
4. Pregnancy.

AEs caused by participation in the study may necessitate modifications to a subject's level of participation or discontinuation of subjects from participation in the study.

Subjects who discontinue early from the study will be replaced.

Subjects who discontinue prematurely from the study for any reason will be encouraged to maintain the follow-up clinic visits that are scheduled after discharge. Study personnel will contact subjects by phone to encourage attendance.

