9 TREATMENT OF SUBJECTS

9.1 Treatments

9.1.1 Description of Study Drug and Dosing Regimen

Dexamethasone is a commercially available synthetic corticosteroid hormone that is used primarily as an anti-inflammatory agent. It is available in tablets (several manufacturers), and as a solution for IV injection (several manufacturers).

Potential AEs, especially when given chronically, include hypertension, hyperphagia, weight gain, hyperglycemia, striae, acne, osteopenia, personality changes, gastrointestinal ulceration and hemorrhage, and growth retardation. Dexamethasone, like other steroids, may cause avascular necrosis of bone.

The dosing of dexamethasone, or an equivalent amount of placebo, is specified in Table 9.1. The initial dose (0.3 mg/kg every 12H) is given for a total of 2 days (4 doses) or until hospital discharge, whichever occurs first. Note: Time Zero is defined as the initial dose of study drug and the first 24 hour period begins with the first dose. All subsequent doses and study assessments are scheduled from this time point. Afterward, all subjects will receive the taper as specified in Table 9.1. All study drug should be given by mouth. If medications temporarily cannot be given by mouth (e.g. NPO status for a diagnostic test or altered mental status) then the temporary administration of the study drug by vein during this time period is acceptable. The dose of IV study drug is the same as the oral formulation. The study drug should be given by mouth as soon as oral medications can be tolerated.

Table 9.1 Dose and Frequency of Study Drug

Dose (mg/kg)	Max single Dose (mg)	Frequency	24hr dose (mg/kg)	Duration (days)	
0.3	12	Every 12H	0.6	2 (or hospital discharge)	} “High Dose”
0.3	12	Every 24H	0.3	2	
0.2	8	Every 24H	0.2	2	} “Taper”
0.1	4	Every 24H	0.1	2	

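### Sections 9.1.1 and 11.7 give opposite instructions for a subject who loses the oral route after entry, and Sections 9.1.2 and 8.4 do not settle which applies

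*Protocol*

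**What the plan says.** **Protocol Section 9.1.1** makes the oral route the norm and then provides for its loss: "If medications temporarily cannot be given by mouth (e.g. NPO status for a diagnostic test or altered mental status"), "the temporary administration of the study drug by vein during this time period is acceptable". The IV dose equals the oral dose, and treatment is to return to the oral route: "The study drug should be given by mouth as soon as oral medications can be tolerated". The same section says that every subject receives the taper after the high-dose phase.

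**Protocol Section 9.1.3** provides active drug and placebo in pre-filled syringes for IV use, so the route can be used without breaking the blind.

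**Protocol Section 11.7** gives a different instruction: "subjects will also have dexamethasone discontinued if they become unable to orally ingest dexamethasone". It does not distinguish temporary from lasting inability and mentions neither the IV route nor a taper. It adds that subjects whose drug is stopped remain under follow-up for side effects.

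**Protocol Section 9.1.2** rules out any other modification or temporary interruption of dosing. For stopping, it points to Section 8.4 and, for a severe AE, to Section 11.8.

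**Protocol Section 8.4** lists four circumstances that require discontinuation. Loss of the oral route is not among them. The section also says: "Subjects who discontinue early from the study will be replaced".

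**The concern.** Entry requires the ability to take capsules, so the question concerns subjects who lose oral intake after entry. For such a subject one section allows dosing to continue by vein and another ends it. A site could follow either and claim compliance.

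Three things depend on which one a site follows:

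- **Exposure.** A stop under Section 11.7 is untapered as written. The regimen was built around a taper because, in the words of Section 6.2, "Abrupt discontinuation of a short course of IV corticosteroid may precipitate an early relapse of VOC".
- **Outcomes tied to dosing.** Rebound hospitalization is a secondary endpoint and is monitored quarterly (Section 11.6.6). The biomarker draws in Section 10.2.1 are timed to the second and fourth doses and to the end of the taper.
- **Counting.** Section 11.7 introduces its criteria as grounds for discontinuation from the study, and Section 8.4 replaces subjects who discontinue early from the study. A site could therefore treat a subject who only stopped study drug as one to be replaced.

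**Working it through.** The protocol states no statistical figure on this point, so the check is a comparison of text plus a measure of the exposure at stake.

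**1. The two rules side by side**

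| | Section 9.1.1 | Section 11.7 |
|---|---|---|
| Trigger | Oral dosing temporarily impossible; examples are NPO for a test and altered mental status | Subject becomes unable to take the drug by mouth; no duration given |
| Action | IV study drug is acceptable (permissive) | Drug will be discontinued (mandatory) |
| Afterwards | Return to oral dosing; taper for all | No taper mentioned; follow-up for side effects |

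A subject with altered mental status after entry meets both triggers, and the actions are opposite.

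**2. Do other sections settle it?**

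- Section 9.1.2 points to Section 8.4, whose required list omits loss of the oral route.
- Section 9.1.2 also points to Section 11.8 for a severe AE, but Section 11.8 is Pregnancy Reporting. If Section 11.7 was meant, the pointer leads back to one side of the conflict. Being NPO for a test is in any case not a severe AE.
- No section sets a time that separates temporary from lasting inability. Inpatient doses are due within 60 minutes of schedule (Section 9.1.2), so staff must act before they know which it is.

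**3. Exposure at stake, from Table 9.1**

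- High-dose phase: 0.6 mg/kg/day × 2 days = 1.2 mg/kg.
- Taper: 0.3 × 2 + 0.2 × 2 + 0.1 × 2 = 1.2 mg/kg.
- Total: 1.2 + 1.2 = 2.4 mg/kg over 2 + 2 + 2 + 2 = 8 days.
- Stopping at the end of the high-dose phase omits 6 of 8 days (75%) and 1.2 of 2.4 mg/kg (50%).
- The maximum single doses do not change that share. At the caps the high-dose phase is 12 × 2 × 2 = 48 mg, and the taper is 12 × 2 + 8 × 2 + 4 × 2 = 48 mg.

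An earlier stop omits more and a later one less. The figures assume a full two-day high-dose phase.

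**4. How many subjects**

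The documents give no rate of loss of the oral route after entry. The number affected, and any effect on power or on the treatment estimate, cannot be computed.

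**The case against.** The best defence is that the two sections cover different cases. Section 9.1.1 is the specific dosing rule for temporary loss, and Section 11.7 can be read as covering lasting loss. Supplying IV syringes would make little sense if every loss of the oral route ended treatment. This reading is plausible and may be what was intended. But Section 11.7 does not say so, and its unqualified wording covers the temporary case too.

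Other parts of the defence stand and limit the point:

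- Section 9.1.1 only permits the IV route; it does not require it.
- Section 13.1 keeps all randomized subjects in the ITT population, and Section 11.7 keeps stopped subjects in follow-up. Replacement adds a subject; it does not remove one from the ITT population.
- The primary endpoint is assessed every 4 hours until discharge (Section 7.1.1), and nothing there ties the assessment to continued dosing.

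A reader might also infer more than the documents support:

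- **That many subjects are affected, mostly in one arm.** Table 5.1 shows clinical deterioration in 14 of 21 placebo and 1 of 22 dexamethasone subjects. The protocol does not define that deterioration as loss of oral intake. The table describes children with mild or moderately severe ACS on untapered IV drug. Moreover, stopping placebo withdraws no steroid, so harm from abrupt withdrawal could arise only in the dexamethasone arm.
- **That Section 9.1.2 forbids any other reason for stopping.** It says drug may be stopped according to the sections it names, and does not call them exclusive. Section 8.4 also allows discontinuation at the investigator's discretion.
- **That the affected subjects are the sickest.** The severe stratum in Section 8.3 includes "impending respiratory failure or need for invasive or non-invasive ventilatory support", but that describes severity before randomization. A subject who is NPO for a test need not have deteriorated at all.

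**Conclusion.** The point holds as an unresolved conflict in the current text. Sections 9.1.1 and 11.7 give opposite actions for a subject who loses the oral route after entry, and Sections 9.1.2 and 8.4 do not decide between them. For a dexamethasone subject stopped at the end of a full high-dose phase, the consequence is loss of the whole taper: 6 of 8 days and half of the planned mg/kg.

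The number of such subjects is unknown. No effect on type I error, power or the primary estimate is shown, so this is a matter of reconciling the protocol's wording and not a flaw in the primary analysis. The conclusion rests on reading Section 11.7 as written. It would fall if another study document already separates temporary from lasting loss of the oral route.

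**What to change.** Reconcile Sections 9.1.1, 9.1.2 (including its pointer to Section 11.8), 8.4 and 11.7 into one rule for loss of the oral route. State it once and refer to it from the other sections. Word it for study drug and not for dexamethasone, so that blinded sites apply it identically in both arms. Which clinical rule is kept, including any limit on duration and what happens to the taper, is for the sponsor's clinicians.

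State in the same place that stopping study drug for this reason is not discontinuation from the study under Section 8.4. The subject is then not replaced and stays in follow-up and in the ITT population. The last two parts confirm what Sections 11.7 and 13.1 already imply; the statement on replacement is new.

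The cost is a wording change and a memo to sites. Blinded IV supply is already planned in Section 9.1.3.
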